10.3.6. PN Associated Pain Intensity and Frequency

Subjects will be asked to report the intensity and frequency of pain they endure related to their PN. Pain intensity is captured using a NRS.

Subjects will rate the frequency of their pain on a 6-point scale (0 = Never, 1 = Less than once a week, 2 = 1-2 Days a week, 3 = 3-4 Days a week, 4 = 5-6 Days a week, 5 = Every day) in response to the following question:

"How often would you say that you experience pain from your skin disease (prurigo nodularis)?"

Subjects will rate the intensity of their pain using an 11-point NRS (0-10) in response to the following question:

This document is confidential.

"On a scale of 0 to 10, with 0 being "no pain" and 10 being "the worst unbearable pain", how would you rate the pain associated with your skin disease (prurigo nodularis) at the worst moment during the past week?"

Summaries using OC will be generated for PN associated pain frequency and intensity at Baseline, Week 4, Week 8, Week 12, Week 16, Week 20, and Week 24 on ITT population. Pain frequency will be summarized as a categorical variable. Pain intensity will be summarized as a continuous variable. Absolute change from Baseline in PN associated pain intensity will also be summarized.

Proportions of subjects with PN associated pain frequency rating = 5 (every day, non-responder) will be presented using missing as non-responder for ITT population up to Week 24.

Additionally, change and percentage from Baseline in PN associated pain intensity will be presented using MMRM model for ITT population up to Week 24.

No hypothesis testing will be performed.

10.3.7. Patient Global Assessment of Disease (PGAD)

For the PGAD, subjects will be asked to rate their overall impression of their skin disease (prurigo nodularis) severity using a 5-point scale (0 = clear, 1 = almost clear, 2 = mild, 3 = moderate, 4 = severe). Subjects will be asked the following question:

"Overall, how would you describe your skin disease (prurigo nodularis) right now?"

PGAD will be collected at Baseline/Day 1, Week 1, Week 16, Week 24 and Early Termination and be summarized for Baseline, Week 1 Week 16, and Week 24 as a categorical variable using OC on the ITT population.

The proportion of subjects reporting low disease activity (clear, almost clear, or mild) based on PGAD will be summarized using OC on the ITT population. The estimate of treatment unadjusted and strata-adjusted differences with the corresponding two-sided 95% CI, and p-values from the CMH test will be presented.

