8.3. Missing Data

The primary method to impute the missing values will be as follows:

Continuous Endpoints: For continuous secondary endpoints (except EQ-5D, HADS) during treatment period, the MI under MAR assumption approach and the MMRM approach will be used to handle the missing data.

Binary Endpoints: All missing values will be treated as a non-responder for the binary endpoints for primary, key secondary and secondary endpoints. To assess the robustness of non-responder analysis for primary and key secondary endpoints, a tipping point analysis will be performed. The MI under MAR assumption, last observation carried forward (LOCF) approach, and observed case (OC) approach will be used as sensitivity analysis to impute the missing values for the primary and key secondary endpoints. If applicable, the continuous response will be imputed first, and the response will then be categorized.

Use of rescue therapy: All efficacy data, except OC, will be treated as treatment failure. Binary endpoints will be based on the underlying values and continuous variables will be imputed using the worst case score (questionnaires) or worst case value (diary data), on or after rescue therapy is used, independent if visit was attended or not. This procedure will be completed before imputing missing data under different assumptions (i.e., non-responder, LOCF, MI under MAR/MNAR). A different approach will be applied for MMRM analysis where data on or after rescue therapy will be considered as missing before applying MMRM analysis.

In OC analysis, no observed data after subject has received rescue treatment will be excluded. There will be no imputations for missing data.

Adverse events and concomitant medications/procedures: Missing assessment times will have imputed times for the purposes of assessing treatment emergence for AEs or classifying medications/procedures into prior/concomitant. However, the assessment date and time (start date, stop date, and time if collected from CRF) without imputation will be presented in the listings.

For the start of a concomitant medication/procedure or AE:

- Only the year is reported: If the subject received the first study drug dose in the year reported, then the date of the first dose of study drug will be used as the start date; otherwise, January 1 of the year reported will be used as the start date.

This document is confidential.

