10.3.8. Patient Global Assessment of Treatment (PGAT)

The PGAT utilizes a 5-point Likert scale (0 = poor, 1 = fair, 2 = good, 3 = very good, 4 = excellent) or subjects to rate the way they feel their skin disease (prurigo nodularis) is responding to the study treatment. Subjects will be asked the following question at Week 16, Week 24 and Early Termination:

"How would you rate the way your skin disease (prurigo nodularis) responded to the study medication?"

PGAT will be summarized as a categorical variable for Week 16 and Week 24 using OC on the ITT population.

The proportion of subjects satisfied with study treatment (good, very good, or excellent) based on PGAT will be summarized using OC on the ITT population. The estimate of treatment unadjusted and strata-adjusted differences with the corresponding two-sided 95% CI, and p-values from the CMH test will be presented.

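### PGAD and PGAT responder rates are tested on observed cases only, although SAP Section 8.3 counts missing secondary binary values as non-response

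*SAP*

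**What the plan says.** Section 8.3 of the SAP gives the general rule for binary endpoints: "All missing values will be treated as a non-responder for the binary endpoints for primary, key secondary and secondary endpoints". The sentence has no exception for PGAD or PGAT. The same section gives observed cases a limited role: the "observed case (OC) approach will be used as sensitivity analysis to impute the missing values for the primary and key secondary endpoints". Section 10.3 adds that secondary endpoints are shown descriptively on observed cases.

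On rescue, Section 8.3 states: "All efficacy data, except OC, will be treated as treatment failure". It then defines OC: "In OC analysis, no observed data after subject has received rescue treatment will be excluded. There will be no imputations for missing data".

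For the two patient global ratings the data basis is different. Section 10.3.7 says that the proportion with low disease activity "based on PGAD will be summarized using OC on the ITT population", and Section 10.3.8 says that the proportion satisfied with treatment "based on PGAT will be summarized using OC on the ITT population". Each then plans unadjusted and strata-adjusted differences with 95% confidence intervals, and "p-values from the CMH test will be presented". In the index of tables, the analysis tables for these endpoints (14.2.3.8.2 for PGAD, 14.2.3.9.2 for PGAT) are both labelled OC. Neither has a missing-as-non-responder counterpart.

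**The concern.** Both proportions are listed secondary efficacy endpoints and will carry p-values. Table 10-1 lists them with a CMH test on the ITT population, like the other responder endpoints, so a reader of that table would assume the same handling of missing data. In fact these two comparisons would be made only among subjects who gave a rating, while the other tested responder rates count every randomized subject.

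Two things are at stake. First, the reported rates of low disease activity and satisfaction would have a denominator that depends on who supplied a rating, and that may differ between arms. Second, choosing OC also switches off the rescue rule, so a favourable rating given after rescue counts as a response. The results could not be set beside the DLQI, SD NRS, PP NRS or IGA response rates as measures of the same kind.

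**Working it through.** **Step 1. Is OC really the basis of the test?** In Sections 10.3.7 and 10.3.8 the reference to OC is attached to the summary sentence, and the sentence on the CMH test names no data set. The table index settles it: the only tables titled as an analysis of these two proportions are the OC ones.

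**Step 2. Comparison with the other tested responder endpoints.**

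| Endpoint (SAP section) | Basis of CMH test |
|---|---|
| IGA success (10.3.1) | non-responder imputation |
| PAS items 5a and 5b (10.3.2) | non-responder imputation |
| PP NRS and AP NRS (10.3.3) | non-responder imputation |
| SD NRS improvement (10.3.4) | non-responder imputation; OC summarized |
| PGAD low disease activity (10.3.7) | OC only |
| PGAT satisfaction (10.3.8) | OC only |
| DLQI improvement (10.3.9) | non-responder imputation; OC summarized |

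**Step 3. Who leaves the denominator?** Section 4.3 plans 180 nemolizumab and 90 placebo subjects and assumes 15% dropout. If every dropout lacked a rating, OC would test 180 × 0.85 = 153 against 90 × 0.85 = 76.5 subjects. About 27 and 13 to 14 subjects whom Section 8.3 counts as non-responders would be left out. This is an upper figure for that dropout rate, because early-termination ratings are placed by Table 8-1 in Week 16 (days 61 to 154) or Week 24 (days 155 to 210) and are used when they fall there.

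**Step 4. Size for missing data.** The SAP gives no expected PGAD or PGAT rates and no missingness by arm, so every rate below is assumed. With observed rates r1 (nemolizumab) and r2 (placebo) and missing fractions m1 and m2:

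- OC difference = r1 − r2
- Non-responder difference = r1(1 − m1) − r2(1 − m2)

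With r1 = 60% and r2 = 30%, the OC difference is 30 points.

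- 15% missing in each arm: 0.60 × 0.85 − 0.30 × 0.85 = 0.510 − 0.255 = 25.5 points. The arm rates fall by 9 and 4.5 points.
- 10% and 25% missing: 0.60 × 0.90 − 0.30 × 0.75 = 0.540 − 0.225 = 31.5 points.

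A smaller assumed effect shows when the inference can change. With observed rates of 45% and 30% at 180/90, and an unstratified two-sided pooled z-test as a stand-in for the CMH test:

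| Missing, nemolizumab / placebo | OC | Non-responder |
|---|---|---|
| 15% / 15% | 15.0 points, p = 0.029 | 12.75 points, p = 0.037 |
| 20% / 5% | 15.0 points, p = 0.025 | 7.5 points, p = 0.22 |
| 10% / 25% | 15.0 points, p = 0.035 | 18.0 points, p = 0.003 |

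**Step 5. Size for rescue.** Assume no missing data, response of 50% and 20% in non-rescued subjects, rescue in 5% and 15%, and a favourable rating from 40% of rescued subjects.

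- OC: (0.95 × 0.50 + 0.05 × 0.40) − (0.85 × 0.20 + 0.15 × 0.40) = 0.495 − 0.230 = 26.5 points
- Rescue as failure: 0.95 × 0.50 − 0.85 × 0.20 = 0.475 − 0.170 = 30.5 points

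Here OC understates the difference relative to the rescue-as-failure rule. Taken together, the examples show no fixed direction.

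**The case against.** The strongest reply is that the plan allows this. Section 10.3 sends binary secondary endpoints to the primary method only where nothing else is specified, and it exempts OC analyses from non-responder imputation. Sections 10.3.7 and 10.3.8 and the table index agree with each other, so a programmer would not be in doubt. HADS and EQ-5D VAS are also tested on observed cases, which suggests that the choice may have been deliberate. This softens the conflict but does not remove it. For continuous endpoints, Section 8.3 names EQ-5D and HADS as exceptions; for binary endpoints it names none. No reason is given for treating PGAD and PGAT differently from DLQI, and Section 14 does not mention it.

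A reader might infer that the rescue handling is a second contradiction, or that it breaches the estimand in Table 7-2. The SAP does not support that. Table 7-2 covers the co-primary endpoints. It is extended to secondary endpoints by a note in Section 10.3 that exempts OC, and Section 8.3 makes the same exemption. The rescue effect follows from making OC the only tested analysis. Nor does OC turn every rescued subject into a success: only a favourable rating counts as a response.

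A reader might also infer that all dropouts are lost. Subjects who stop study drug are asked to attend all remaining visits (Section 4.1), and both ratings are collected at early termination, so some dropouts will contribute a value.

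Finally, non-responder imputation is itself an assumption and not the truth, and scoring an unanswered PGAT as dissatisfied is a convention. That is fair, but it is the convention that this SAP adopts for its binary endpoints.

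**Conclusion.** The point stands as an unexplained departure from the SAP's own rule on missing binary data. It affects two secondary endpoints whose only planned test, confidence interval and p-value rest on observed cases. Subjects without a rating in the analysis window leave the comparison, and favourable ratings after rescue count as responses.

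The size cannot be fixed from the SAP. Under the assumed 60% and 30%, the difference moves from 30 points to between 25.5 and 31.5, depending on missingness. Under a smaller assumed effect with unequal missingness, nominal significance can be lost or strengthened. These figures rest on assumed rates, on missing ratings at or around the planned 15% dropout, and on an unstratified test. They show that the choice matters, not which arm it favours.

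PGAD and PGAT lie outside the fixed testing sequence in Section 10, so the primary and key secondary conclusions and their type I error are untouched. The change should be made, but it does not threaten the trial's main result.

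**What to change.** In Sections 10.3.7 and 10.3.8, state that the CMH test, the differences and the confidence intervals use missing as non-responder and rescue as failure, as Section 8.3 sets out and as Section 10.3.9 does for DLQI. Keep OC as the descriptive summary or as a supplementary analysis. Retitle Tables 14.2.3.8.2 and 14.2.3.9.2 accordingly, or add a non-responder table for each endpoint beside them.

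If the sponsor prefers OC as the tested basis, the minimum is to name PGAD and PGAT as exceptions in Section 8.3 and give the reason. That would remove the inconsistency, but the two results would still not be comparable with the other responder endpoints.

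The cost is a few sentences and two table titles. The downside of the main change is that the reported response rate in each arm becomes somewhat lower; the treatment difference may move in either direction.

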10.3.8. Patient Global Assessment of Treatment (PGAT)

The PGAT utilizes a 5-point Likert scale (0 = poor, 1 = fair, 2 = good, 3 = very good, 4 = excellent) or subjects to rate the way they feel their skin disease (prurigo nodularis) is responding to the study treatment. Subjects will be asked the following question at Week 16, Week 24 and Early Termination:

"How would you rate the way your skin disease (prurigo nodularis) responded to the study medication?"

PGAT will be summarized as a categorical variable for Week 16 and Week 24 using OC on the ITT population.

The proportion of subjects satisfied with study treatment (good, very good, or excellent) based on PGAT will be summarized using OC on the ITT population. The estimate of treatment unadjusted and strata-adjusted differences with the corresponding two-sided 95% CI, and p-values from the CMH test will be presented.

10.3.9. Dermatology Life Quality Index

The DLQI is a validated 10-item questionnaire covering domains including symptoms/feelings, daily activities, leisure, work/school, personal relationships, and treatment.

This document is confidential.

The subject will rate each question ranging from 0 (not at all) to 3 (very much). The DLQI total score is calculated by summing each questionnaire. Total score will have a maximum score of 30 and a minimum of 0. The higher the score, the more quality of life is impaired.

DLQI will be collected at Baseline/Day 1, Week 4, Week 16, Week 24 and Early Termination. DLQI total score will be summarized as a continuous variable using OC on the ITT population for Baseline, Week 4, Week 16 and Week 24. Absolute change from Baseline in DLQI total score will also be summarized.

Absolute change from Baseline in DLQI total score at Week 4, Week 16 and Week 24 will be analyzed using ANCOVA with MI assuming MAR for missing data including treatment group, analysis center and body weight at randomization cut-off (< 90 kg and ≥ 90 kg) as factor and baseline as covariate, and using MMRM, including visit, treatment group, analysis center and body weight at randomization cut-off (< 90 kg and ≥ 90 kg) as factor, baseline, the interaction term between baseline and visit, and the interaction term between treatment group and visit as covariates on ITT population. The LSMeans, standard error of LSMeans, and 95% CI for change from baseline, as well as the difference in LSMeans between the treatment groups, the two-sided 95% CI, and associated p-value will be presented on ITT population.

Improvement of ≥ 4 in DLQI will be calculated using Baseline as the reference point for change in DLQI total score. The proportion of subjects with an improvement of ≥ 4 will be summarized on the ITT population using OC and non-responder imputation. The estimate of treatment unadjusted and strata-adjusted differences with the corresponding two-sided 95% CI, and p-values from the Cochran-Mantel-Haenszel test using non-responder will be presented for ITT population.

A line plot for proportion of subjects with DLQI improvement ≥ 4 using non-responder imputation will be presented on the ITT population.

10.3.10. Hospital Anxiety and Depression Scale (HADS)

HADS is a 14-question validated questionnaire completed by the subject. Each question has a multiple choice answer which is scored between 0 and 3. Questions are identified as relating to anxiety (A) or depression (D) and a summation for each area is performed leading to a total score of 0 to 21 for each area. Scores of 0 to 7 are considered normal, 8 to 10 are borderline, and ≥ 11 indicate clinical effects.

HADS will be collected at Baseline/Day 1, Week 16, Week 24 and Early Termination and subscales will be summarized separately for each subscale (Total Score Anxiety and Total Score Depression) as continuous variable using OC for Baseline, Week 16 and Week 24 on the ITT population. Absolute change from Baseline in HADS subscale scores will also be summarized.

Absolute change from Baseline in HADS subscale scores will be analyzed for Week 16 and Week 24 using ANCOVA using observed case, including treatment group, analysis center and body weight at randomization cut-off (< 90 kg and ≥ 90 kg) as factor and baseline as covariate. The LSMeans, standard error of LSMeans, and 95% CI for change from baseline, as well as the difference in LSMeans between the treatment groups, the two-sided 95% CI, and associated p-value will be presented.

10.3.11. EuroQoL 5 Dimension Instrument

The EQ-5D instrument is a validated questionnaire, completed by the subject and consists of 2 parts. The first part consists of 5 multiple choice QoL questions and the second is a 100 point VAS scale with 0 being “Worst imaginable health state” and 100 being “Best imaginable health state”.

This document is confidential.

EQ-5D VAS will be collected at Baseline/Day 1, Week 16, Week 24 and Early Termination and be summarized as a continuous variable using OC for Baseline, Week 16 and Week 24 on the ITT population. Absolute change from Baseline in EQ-5D VAS will also be summarized using OC.

Absolute change from Baseline in EQ-5D VAS at Week 16 and Week 24 will be analyzed using ANCOVA using observed case, including treatment group, analysis center and body weight at randomization cut-off (< 90 kg and ≥ 90 kg) as factor and baseline as covariate. The LSMeans, standard error of LSMeans, and 95% CI for change from baseline, as well as the difference in LSMeans between the treatment groups, the two-sided 95% CI, and associated p-value will be presented.

Five dimensions of EQ-5D (mobility, self-care, usual activities, pain/discomfort, and anxiety/depression) will be summarized as a categorical variable using OC.

10.3.12. Rescue Therapy Used

Subjects who used either medication or procedure as rescue therapy will be summarized using OC.

The number and percentage of subjects receiving any concomitant rescue therapy will be summarized by rescue treatment type (topical, phototherapy, systemic, intralesional corticosteroids, and corresponding subgroups), preferred term within treatment type and overall. The number and percentage of subjects receiving any concomitant procedure of rescue therapy will be summarized by rescue treatment type (phototherapy), preferred term within treatment type and overall.

In addition, the time to first rescue therapy use will be calculated. The data will be analyzed using Kaplan-Meier methodology by presenting the point estimates of the quartiles estimates with the corresponding 95% CI. Kaplan-Meier estimates of time to first rescue therapy use will be summarized by visit. Subjects who do not use any rescue therapy will be censored for the analysis and the end of treatment period will be used as the censoring date. Subjects who discontinued without intake of rescue therapy will also be censored as described above. A Kaplan-Meier curve will also be provided.

Selected Prior Prurigo Nodularis medications and procedures will also be presented.

This document is confidential.

11. Pharmacokinetics

The serum concentration of Nemolizumab will be assessed at Baseline, Week 4, Week 8, Week 12, Week 16, Week 24, Week 32 Follow-up and Early Termination visit. PK analyses are required during any unscheduled visit conducted for safety reasons. As a guideline, PK samples should be collected at approximately the same time of day throughout the study, to the extent possible, before study drug injection (pre-dose samples).

11.1. Pharmacokinetic Concentration Presentation

Serum concentration data (unit: ng/mL) will be summarized on the PK analysis population by visit and by body weight at baseline cut-off (< 90 kg or \geq 90 kg) from Baseline to Week 32, using the following statistics: arithmetic mean, SD, coefficient of variation (CV), geometric mean, geometric CV, median, minimum, maximum, 95% CI of the arithmetic mean, and number below the limit of quantification (BLQ).

Mean and individual (spaghetti plot) serum concentration(s) will be plotted by visit and by body weight at baseline cut-off (< 90 kg or \geq 90 kg) on both a linear and semi-logarithmic scale on the PK analysis population (2 plots).

Individual serum concentrations will be listed on the PK analysis population.

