Subjects who prematurely discontinue the study drug will be asked to continue participation in the study and return for all remaining visits and assessments (including daily assessment of pruritus and sleep disturbance). Subjects who discontinue study drug due to required rescue therapy may be eligible to participate in the LTE study following completion of study visits through Week 24. Subjects who discontinue the study prematurely should complete an early termination (ET) visit and a follow-up visit 12 weeks after the last study drug injection.

As no approved medicine for PN exists with which to compare Nemolizumab, a placebo-controlled design was implemented in this study to allow blinding, randomization, and identical administration procedures to control for human bias or other influences on the disease (e.g., natural disease course), while enabling demonstration of differences in clinical effect and safety profile of investigational treatment, if present. All subjects will have access to rescue medication to minimize risk and for ethical considerations. It is the position of the Committee for Medicinal Products for Human Use (CHMP) that, where ethical and feasible, a placebo control arm should be included in the pivotal trial(s) used to support marketing authorization application.

A 16-week treatment period is considered adequate to evaluate the efficacy and safety of Nemolizumab based on the results of the phase 2a study (RD.03.SPR.115828) in subjects with PN. A further 8-week treatment period is included to provide additional data as requested by the European Medicines Agency for chronic diseases such as PN. All subjects who complete the treatment period (Week 24 visit) can be considered for LTE study eligibility. A 2-to-1 randomization is selected to minimize the number of subjects exposed to placebo for an extended period of time.

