Although the pathophysiology of PN is still not fully understood, the efficacy endpoints selected for the phase 3 trial are relevant to the underlying manifestations associated with the disease under study (i.e., skin lesions, chronic itch, sleep disturbance, and quality of life impairment). The selected endpoints for assessing the safety and PK of Nemolizumab (CD14152) are in accordance with current standards. Blinding subjects and the designated study team to the treatment assignment(s) helps ensure objectivity and minimize bias. Randomization through the Interactive Response Technology (IRT) guards against selection bias.

The study includes an 8-week follow-up period (i.e., 12 weeks after the last study drug injection) for subjects who decline or are not eligible to enroll in the LTE study. The duration of the follow-up period from the final Nemolizumab dose (12 weeks) corresponds to approximately 5 half-lives of Nemolizumab, which is

This document is confidential.

considered adequate to ensure subject safety. The follow-up visit is not required for subjects who participate in the LTE, where the primary objective is long-term evaluation of safety.

Differences may be detectable during the study drug reconstitution process between active study drug and placebo but appear similar after reconstitution is complete (approximately 10 minutes). Throughout the study, a pharmacist (or other qualified personnel) will prepare study drug for injection, including confirmation of complete reconstitution, prior to delivery of study drug for injection. The pharmacist (or other qualified personnel) preparing study drug should not be involved with any study assessments and should not discuss any aspects of study drug reconstitution with the subject or study staff involved in subject interviews or study assessments.

The placebo-controlled design includes a provision for rescue therapy for pruritus, based on the investigator's clinical judgment. Subjects requiring rescue therapy may be eligible for the LTE study but will be required to continue scheduled study visits until the Week 24 visit before LTE eligibility will be assessed.

To avoid bias and to ensure the integrity of the blind, personnel directly involved with the ongoing conduct of the study from the Sponsor, blinded statistical team at Syneos Health, or other investigational study centers will not have access to any information that may lead to unblinding.

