If a study visit occurs outside the visit window, study drug injection(s) can still be administered provided there is a minimum of 3 weeks but not more than 5 weeks since the last injection. If beyond 5 weeks, the next study drug injection should then occur at the next planned visit. Future visits should be scheduled as soon as possible and within the required windows based on the baseline/Day 1 visit date, while maintaining the minimum 3-week interval between 2 injections.

This document is confidential.

5. Endpoints

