6.5. Pharmacokinetic Analysis Population

The PK analysis population will consist of all subjects included in the SAF, with at least one measurable post-baseline PK assessment. Similar to SAF, the treatment group assignment in this population will be defined by the treatment actually received. This population will be used for the descriptive analyses of PK concentrations.

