Week 2	15	8 to 14	9 to 15
Week 3	22	15 to 21	16 to 22
Week 4	29	22 to 28	23 to 29
Week 5	36	29 to 35	30 to 36
Week 6	43	36 to 42	37 to 43
Week 7	50	43 to 49	44 to 50
Week 8	57	50 to 56	51 to 57
Week 9	64	57 to 63	58 to 64
Week 10	71	64 to 70	65 to 71
Week 11	78	71 to 77	72 to 78
Week 12	85	78 to 84	79 to 85
Week 13	92	85 to 91	86 to 92
Week 14	99	92 to 98	93 to 99
Week 15	106	99 to 105	100 to 106
Week 16 ^b	113	106 to 112	107 to 113
Week 17	120	113 to 119	114 to 120
Week 18	127	120 to 126	121 to 127
Week 19	134	127 to 133	128 to 134
Week 20	141	134 to 140	135 to 141
Week 21	148	141 to 147	142 to 148
Week 22	155	148 to 154	149 to 155
Week 23	162	155 to 161	156 to 162

This document is confidential.

Week 24	169	162 to 168	163 to 169
---------	-----	------------	------------

^a If there are less than 4 non-missing assessments within last 7 days prior to the first dose, the interval lower bound will be extended up to 7 additional days, one day at a time, to obtain the most recent 4 non-missing values. The extension will not be applied for the sensitivity analysis by using a minimum of 2 (or 3) daily scores out of the 7 days.

^b If there are less than 4 assessments during Week 16 visit window, upper bound of the visit window (106 - 112) or (107 - 113) will be extended for 5 additional days. If there are still less than 4 assessments after extending upper bound of the visit window, lower bound of the visit window will be extended for another 5 days until 4 assessments are reached.

* For diary data, if the intake date of rescue therapy is before and on the last day of the weekly visit window, this week will be treated as treatment failure except for OC analysis and the weekly average will be imputed using the worst case value, see [Section 8.3](#). For MMRM analysis, values will be considered as missing.

Safety and pharmacokinetics data will not be windowed for by-visit summary. i.e., scheduled visit data will be used for analysis.

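### The by-visit concentration summary does not separate on-schedule samples from those taken after a missed injection or after study drug was stopped, which pulls the Week 8 to Week 24 means down

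*SAP*

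**What the plan says.** Section 11.1 defines the display: "Serum concentration data (unit: ng/mL) will be summarized on the PK analysis population by visit and by body weight at baseline cut-off", running from Baseline to Week 32. The statistics include "arithmetic mean, SD, coefficient of variation (CV), geometric mean, geometric CV, median, minimum, maximum, 95% CI of the arithmetic mean" and the number below the quantification limit. Mean and individual plots on linear and semi-logarithmic scales, and a listing, are also planned.

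Which samples enter is settled by two other sections. Section 6.5 selects subjects, not samples: "The PK analysis population will consist of all subjects included in the SAF, with at least one measurable post-baseline PK assessment". Section 8.4 selects by nominal visit: "Safety and pharmacokinetics data will not be windowed for by-visit summary. i.e., scheduled visit data will be used for analysis". Section 11 places PK sampling at Baseline, Weeks 4, 8, 12, 16, 24 and 32 and at early termination, before injection where possible.

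Two provisions let off-drug samples arise at scheduled visits. Section 4.1: "Subjects who prematurely discontinue the study drug will be asked to continue participation in the study and return for all remaining visits and assessments". The notes to the schedule in Section 4.6, on late visits: "If beyond 5 weeks, the next study drug injection should then occur at the next planned visit".

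Sections 2.1 and 11.2 keep PK parameters, population PK and PK/PD results out of the CSR tables and place them in a separate modeling report.

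**The concern.** A concentration summary by visit is normally read as the level reached under the planned schedule. Here a Week 16 row could average subjects sampled four weeks after an injection with subjects whose last injection was eight, twelve or sixteen weeks earlier. Retaining data after discontinuation fits the treatment-policy handling of efficacy in Section 7, but a concentration depends directly on time since dose.

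Elsewhere the SAP does draw this line. Section 8.2 ends the treatment period of an early discontinuer no later than 28 days after the last dose, and Sections 9.4, 9.5 and 13.1 apply a matching cut to procedures, medications and adverse events. The concentration summary has no such cut.

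PK is a secondary objective (Section 3.2) and serum concentration is its only endpoint (Section 5.4). With the modeling reported elsewhere, this table and its plots are the PK result in the CSR tables and figures. They are also split at 90 kg, the cut-off that defines the two dosing schedules. If off-drug shares differed between the weight groups, that difference would be mixed into the contrast a reader draws from the rows.

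**Working it through.** The plan states no figure for this quantity, so there is nothing to reproduce. The steps below check that the samples enter, then illustrate the size.

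**Do the samples enter?** A subject who stops drug returns for remaining visits and assessments (4.1). One measurable post-baseline value admits the subject (6.5). Scheduled-visit data are used as they stand (8.4) and summarized by visit (11.1). No section excludes, flags or separately tabulates samples by time since injection. Inclusion follows from these sections together, though no single sentence states it.

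**Half-life.** Section 4.1 says that 12 weeks "corresponds to approximately 5 half-lives of Nemolizumab". So the half-life is 12/5 = 2.4 weeks, or 84/5 = 16.8 days.

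**Level of a late sample.** Assume mono-exponential decay and dosing every 4 weeks. Relative to the level 4 weeks after an injection, a sample k intervals late holds r = 2^(−4k/2.4):

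- k = 1 (8 weeks after the last injection): r = 0.315
- k = 2 (12 weeks): r = 0.099
- k = 3 (16 weeks): r = 0.031

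Every subject in the set received at least one injection, normally at baseline. At Week 8 a sample can therefore be at most one interval late, at Week 12 at most two and at Week 16 at most three.

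**Effect on the means.** With a share f of late samples, the arithmetic mean ratio is 1 − f(1 − r) and the geometric mean ratio is r^f. The SAP gives no value for f; 2% to 15% is an assumed range.

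| f | Arithmetic, k = 1 | Geometric, k = 1 | Arithmetic, k = 3 | Geometric, k = 3 |
|---|---|---|---|---|
| 2% | 0.986 | 0.977 | 0.981 | 0.933 |
| 5% | 0.966 | 0.944 | 0.952 | 0.841 |
| 10% | 0.931 | 0.891 | 0.903 | 0.707 |
| 15% | 0.897 | 0.841 | 0.855 | 0.595 |

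Example, f = 15% and k = 1: arithmetic 1 − 0.15 × 0.685 = 0.897; geometric 0.315^0.15 = 0.841.

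**Sensitivity to the half-life.** For assumed half-lives of 2 and 3 weeks, r at k = 1 is 0.250 and 0.397. At f = 15% the arithmetic ratio is then 0.888 and 0.910, and the geometric ratio 0.812 and 0.871.

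**Median and spread.** In a log-normal simulation with an assumed between-subject CV of 50%, the median falls about 1% to 10% over f = 2% to 15%. At k = 1 the geometric CV rises from 0.50 to between 0.53 and 0.69.

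**The case against.** The best reply is that the table has no target from which it could be biased. The endpoint is serum concentration, summarized descriptively. The SAP speaks of pre-dose samples and never promises a trough or steady-state level. As a summary of everything observed the table is correct. No test compares the weight groups, and exposure inference sits in the separate modeling plan, which is not shown to be affected. Section 2.1 also gives the definition of the PK population to a designated CRO, so further handling rules may exist in a document not at hand. The spread statistics, individual plots, concentration listing and missed-dose counts (Section 9.6) would let a careful reader see some of the mixing.

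Much of this stands. It limits the point to one descriptive table and its plots and rules out calling the values wrong. It does not remove the point, because the rows are not labelled as including off-drug samples and the plan offers no display that separates them.

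A reader might also infer a larger effect by taking the 15% in Section 4.3 as the off-drug share and placing every such sample 12 weeks after the last injection. The document does not support this. The 15% is dropout, and subjects who leave the study give no later scheduled-visit samples. The share needed is of those who stop drug but stay, and none is given. A 12-week gap cannot occur at Weeks 4 or 8 and at Week 12 would require that only the baseline dose was given.

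**Conclusion.** The point holds as a lack of separation. As written, the Week 8, 12, 16 and 24 rows and mean plots combine on-schedule and off-drug samples, and their means are lower than on-schedule levels whenever such samples occur. The direction is secure. The SAP gives no rule for how values below the quantification limit enter the means; setting them to missing would shrink the shift without reversing it.

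The size is not secure. If 2% to 15% of samples are one interval late, the fall is about 1% to 10% in the arithmetic mean and 2% to 16% in the geometric mean, and larger with more missed doses. This rests on the implied 16.8-day half-life, mono-exponential decay and an assumed off-drug share. At the low end it is negligible.

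A reader might conclude that the SAP reports biased trough levels or that exposure in one weight group is understated against the other. Neither follows: the SAP does not call these values troughs, and nothing in it shows that discontinuation differs by weight. Week 4 is essentially unaffected, Week 32 is off drug by design, and efficacy analyses are untouched.

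**What to change.** In Section 11.1, define a sample-level flag from the dosing and sampling dates already collected. Base the main Week 8 to Week 24 statistics and mean plots on samples for which the preceding scheduled injection was given and study drug had not been permanently discontinued. Keep every such sample taken within the protocol visit windows, including Week 24 samples after the Week 20 injection. Show off-drug and missed-dose samples in their own rows, flag them in the listing, and keep the all-samples table as supportive.

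Two simpler rules should be avoided. Requiring samples to be pre-dose would empty the Week 24 row, because Section 4.1 puts the last injection at Week 20. Borrowing the 3-to-5-week interval from the notes in Section 4.6 would misapply a rule on the gap between injections. With ±7 days at both visits, a compliant Week 24 sample can fall from 162 − 148 = 14 to 176 − 134 = 42 days after the Week 20 injection, so compliant samples would be dropped.

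The cost is a few lines of SAP text and one derived variable, with no change in conduct. The drawback is a slightly smaller n at later visits, and the main rows then describe subjects still on schedule, which the table should state.
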